#### **Description of Potential Risks**

There is a risk of thrombosis when subjects, with either congenital or acquired deficiency, are treated with human fibrinogen particularly with high dose or repeated dosing. Subjects given human fibrinogen should be observed closely for signs or symptoms of thrombosis. In subjects with a history of coronary heart disease or myocardial infarction, in subjects with liver disease, in peri- or post-operative subjects, in neonates, or in subjects at risk of TEEs or DIC, the potential benefit of treatment with human plasma fibrinogen should be weighed against the risk of thromboembolic complications. Caution and close monitoring should also be performed.

Acquired hypofibrinogenaemia is associated with low plasma concentrations of all coagulation factors (not only fibrinogen) and inhibitors and so treatment with blood products containing coagulation factors should be considered. Careful monitoring of the coagulation system is necessary.

If allergic or anaphylactic-type reactions occur, the injection/infusion should be stopped immediately. In case of anaphylactic shock, standard medical treatment for shock should be implemented.

There is currently no data on fibrinogen inhibitors available with human fibrinogen.

Standard measures to prevent infections resulting from the use of medicinal products prepared from human blood or plasma include selection of donors, screening of individual donations and plasma pools for specific markers of infection and the inclusion of effective manufacturing steps for the inactivation/removal of viruses. Despite this, when medicinal

products prepared from human blood or plasma are administered, the possibility of transmitting infective agents cannot be totally excluded. This also applies to unknown or emerging viruses and other pathogens.

The measures taken are considered effective for enveloped viruses such as human immunodeficiency virus (HIV), hepatitis B virus (HBV) and hepatitis C virus (HCV) and for the non-enveloped hepatitis A and parvovirus B19 viruses. Every time that fibrinogen is administered to a patient, the name and batch number of the product are to be recorded in order to maintain a link between the patient and the batch of the product.

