7.2.3 Safety

Safety and tolerability in this clinical study will be addressed by the following safety parameters:

- Frequency, severity, seriousness and causality of AEs.
- Changes in vital signs (including pulse [heart rate], blood pressure, respiratory rate, body temperature).
- Change in clinical laboratory assessments of hematology, clinical chemistry and urinalysis.
- Change in clinical laboratory assessments of markers of coagulation:

Prothrombin time (PT)/International Normalized Ratio (INR), activated partial thromboplastin time (aPTT), thrombin-antithrombin III complex (TAT), prothrombin fragments 1+2 (F1+2), D-dimer, protein S (PS), protein C (PC), antithrombin III (AT III), thrombin time (TT) and Endogenous Thrombin Potential (ETP) measured by Thrombin Generation Test (TGT) (TGT only for subjects undergoing cytoreductive PMP surgery).

• Change in clinical laboratory assessments of coagulation factors:

Factor II (FII), factor V (FV), factor VII (FVII), factor VIII (FVIII), factor IX (FIX), factor X (FX), factor XI (FXI), factor XIII (FXIII) and von Willebrand factor (vWF) (vWF only for subjects undergoing cytoreductive PMP surgery).

- Frequency, severity, seriousness and causality of thromboses and TEEs, of relevant bleeding complications, of Hypersensitivity/ anaphylactic reactions, and of bleeding related ischaemic events.
- Change in viral status.

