12.6.1 Adverse Events

Adverse events will be coded using the most updated version of the MedDRA® dictionary.

Adverse events occurring during or after the administration of study medication are TEAEs. If a partially missing AE start date is imputed, the imputed date will be used to assess if the AE is treatment emergent. If AE start date is completely missing and AE end date/time is after IMP start date/time or if it is completely missing, then it is a TEAE. All other AEs are regarded non-treatment emergent.

The search criteria for the adverse events of special interest are specified in the table below:

AESI	Search Criteria
Thrombosis or TEE	SMQ: Embolic and thrombotic events (narrow)
Relevant bleeding complication	All AESIs ticked as AESI, but not falling under categories "Thrombosis or TEE" or "Suspicion of transmission of infective agents (viral safety)"
Suspicion of transmission of infective agents (viral safety)	Preferred terms: "transmission of infectious agent via product" and "suspected transmission of infectious agent via product"

Adverse events related to Hypersensitivity/anaphylactic reactions/anaphylactic shock will be selected by using the following criteria: SMQ: Hypersensitivity, (narrow), Anaphylactic reaction (narrow), and Anaphylactic shock conditions (narrow).

Adverse events related to bleeding related ischaemic events will be selected by using the following criteria: SMQ: Ischaemic heart disease: Myocardial infarction (narrow), Other ischaemic heart disease (narrow); Ischaemic colitis (broad); Ischaemic central nervous system vascular conditions (narrow); Embolic and thrombotic events, arterial (narrow); Embolic and thrombotic events, venous (narrow); PT: Peripheral ischaemia; Ischaemia; Gastric ischaemia; Hepatic ischaemia; Ischaemic contracture of the left ventricle; Dry gangrene; Ischaemic gastritis; Ischaemic limb pain; Necrosis ischaemic; Spleen ischaemia; Uterine ischaemia.

If a serious adverse event (SAE) occurs in a subject after the period of observation, i.e., after the last study visit, and is considered by the investigator to be related to the study medication, this should still be recorded as a SAE. If the eCRF has been closed for the subject, the investigator should contact the sponsor to determine how to report the SAE.

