The total number and percentage of subjects reporting at least one AE and the absolute count of AEs will be tabulated for each treatment, treatment arm and overall once for the overall trial population and separately by type of surgery (spinal and abdominal surgery), sex and race. The initial summary will also provide a breakdown of the following:

- Any AE
- Any non-severe AE
- Any TEAE
- Any NTEAE
- Any non-serious TEAE
- Any non-severe TEAE
- Any treatment-related TEAE
- Any severe AE
- Any severe TEAE
- Any severe treatment-related TEAE
- Any SAE
- Any serious TEAE
- Any serious treatment-related TEAE
- Any AESI
- Any treatment-emergent AESI
- Any treatment-emergent treatment-related AESI
- Any AE leading to discontinuation from study
- Any TEAE leading to discontinuation from study

- Any treatment-related TEAE leading to discontinuation from study
- Any AE with outcome of death
- Any TEAE with outcome of death
- Any treatment-related TEAE with outcome of death
- Any TEAE of special interest
 - Thrombosis or TEE
 - Suspicion of transmission of infective agents
 - Relevant bleeding complication
- Any TEAE of Hypersensitivity/ anaphylactic reactions/ anaphylactic shock
- Any TEAE of Bleeding related ischaemic events

The number of events, number and percentage of subjects reporting AEs will be tabulated (as well for causality and maximum severity) in the following way once for the overall population, and separately by type of surgery (spinal and abdominal surgery) and sex in the following:

- Treatment-emergent AEs by system organ class and preferred term
- Serious treatment-emergent AEs by system organ class and preferred term
- Causally related TEAE by system organ class, preferred term and maximum severity
- Not Causally related TEAE by system organ class, preferred term and maximum severity
- Causally related Serious TEAE by system organ class, preferred term and maximum severity
- Not Causally related Serious TEAE by system organ class, preferred term and maximum severity

The number of events, number and percentage of subjects reporting AEs will be tabulated (as well for causality and maximum severity) in the following way once for the overall population, and separately by type of surgery (spinal and abdominal surgery) in the following:

- Non-treatment emergent AEs by system organ class and preferred term (will not be tabulated for maximum severity or causality)

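### The SAP search for bleeding related ischaemic events takes in thromboembolic queries with no link to bleeding, so its summary row and table total cannot be read as labelled

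*SAP*

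**What the plan says.** SAP 7.2.3 lists among the safety parameters the frequency, severity, seriousness and causality "of thromboses and TEEs, of relevant bleeding complications, of Hypersensitivity/ anaphylactic reactions, and of bleeding related ischaemic events". Thromboses and bleeding related ischaemic events are thus named as different items.

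SAP 12.6.1 then gives the search rules:

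- **Thrombosis or TEE** (an adverse event of special interest, AESI): "SMQ: Embolic and thrombotic events (narrow".
- **Relevant bleeding complication** (also an AESI): "All AESIs ticked as AESI, but not falling under categories" for thrombosis or TEE, or for suspected transmission of infective agents.
- **Bleeding related ischaemic events** (outside the AESI table): "Adverse events related to bleeding related ischaemic events will be selected by using the following criteria". The list holds queries for ischaemic heart disease, ischaemic colitis and ischaemic central nervous system conditions, then "Embolic and thrombotic events, arterial (narrow); Embolic and thrombotic events, venous (narrow", then a set of ischaemia preferred terms.

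The ischaemic category feeds a line in the overall summary, "Any TEAE of Bleeding related ischaemic events", and a table by system organ class and preferred term, overall and by type of surgery. Thrombosis or TEE has its own summary line and its own tables.

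On the clinical background, Protocol 6.11 states: "There is a risk of thrombosis when subjects, with either congenital or acquired deficiency, are treated with human fibrinogen".

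**The concern.** The label announces ischaemia that arises from bleeding, but the search would also pick up a post-operative clot with no bleeding behind it. On the ordinary reading of the labels, the two headings describe different failures. One is clotting after fibrinogen substitution, a named risk of the product class. The other is ischaemia where haemostasis was inadequate. These can move in different directions between the arms.

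The venous query is the hardest to explain: nothing in either document says why a venous thrombosis should count as bleeding related ischaemia. What is at stake is whether a reader can learn anything about bleeding-related ischaemia from the row and table that carry that name. Protocol section 1 expects a safety advantage of BT524 to enter the risk-benefit assessment, so a safety row that cannot be read as labelled is worth correcting.

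**Working it through.** The plan states no expected number of events on this point, so there is no figure to reproduce. The check compares the search rules and then illustrates the effect with assumed counts.

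**1. Overlap.** The AESI uses the narrow embolic and thrombotic events query. The ischaemic search uses the arterial and venous queries of the same name, also narrow. By construction, every treatment-emergent event coded to either one enters the ischaemic category. By query name, it also enters thrombosis or TEE. The term lists are not reproduced in the documents, so the membership of any single term is inferred from the query name.

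**2. Is there a filter?** None is given. SAP 12.6.1 removes TEEs from relevant bleeding complications but has no matching rule for the ischaemic category. Protocol 9.3.1 requires a relevant bleeding complication to be caused by bleeding; no such condition applies to the category with bleeding in its name. The protocol's own lists of AESIs (9.3.1) and safety endpoints (9.2.3) do not contain the ischaemic category, so nothing there narrows the search.

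**3. Size.** Let I be events from the ischaemia queries and terms alone, and T be events from the two thromboembolic queries. Assume one event per subject, no event in both sets, and equal arms (the plan aims at 100 evaluable subjects per arm), so that a ratio of counts equals a ratio of proportions.

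- Row as written, per arm: I + T
- Ratio without the thromboembolic queries: I(BT524) / I(comparator)
- Ratio as written: [I(BT524) + T(BT524)] / [I(comparator) + T(comparator)]

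All counts are assumptions, BT524 v comparator:

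| I | T | Row as written | Ratio, I only | Ratio as written |
|---|---|---|---|---|
| 1 v 5 | 6 v 2 | 7 v 7 | 1/5 = 0.20 | 7/7 = 1.00 |
| 2 v 5 | 6 v 3 | 8 v 8 | 2/5 = 0.40 | 8/8 = 1.00 |
| 1 v 4 | 3 v 3 | 4 v 7 | 1/4 = 0.25 | 4/7 = 0.57 |
| 1 v 4 | 5 v 5 | 6 v 9 | 1/4 = 0.25 | 6/9 = 0.67 |
| 1 v 4 | 10 v 10 | 11 v 14 | 1/4 = 0.25 | 11/14 = 0.79 |
| 2 v 2 | 6 v 3 | 8 v 5 | 2/2 = 1.00 | 8/5 = 1.60 |

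The first two lines show masking when the effects oppose each other. The next three show that opposite effects are not needed: equal TEE counts pull the ratio towards 1. In the last line a TEE imbalance alone appears as an excess of bleeding related events.

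**4. What is unaffected.** In every line the thrombosis or TEE row still shows T as it occurred, for example 6 v 2 in the first.

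**The case against.** The case for leaving the search alone has real substance.

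- Thrombosis or TEE is tabulated on its own by system organ class and preferred term, overall, by surgery type and by sex, with severity and causality for the overall and surgery-type tables. This stands. A reader might infer that opposite safety signals cancel and that both are hidden; the documents do not support that. The TEE signal is reported in full.
- The ischaemic table is itself split by preferred term, so clot terms and ischaemia terms fall on separate lines, and all adverse events are listed with time to onset. This also stands. It confines the problem to the aggregate row and the table total, which a careful reader could partly reconstruct.
- Failure of haemostasis is also captured by relevant bleeding complications, rebleeds, blood loss and transfusion. True, but none of these measures ischaemia, which is what this category was added to show.
- A reader might call this double counting. No total in the SAP adds the two headings together, and the SAP nowhere says they are mutually exclusive. The accurate statement is that an event can appear under both.
- A reader might conclude that every deep vein thrombosis or pulmonary embolism is declared a consequence of bleeding. The SAP makes no event-level attribution, and the query term lists are not in the documents.
- The counts are invented. They show what can happen, not how likely it is.

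After these concessions, the row and table total still do not measure what their label says.

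**Conclusion.** The point holds, limited to the aggregate row for bleeding related ischaemic events and the total of its table, including the total within each surgery type. Followed as written, the search gives a mixture of ischaemic and thromboembolic events under a bleeding label. Under the assumed counts above, a real difference in ischaemic events can vanish (7 v 7) or shrink (0.25 to between 0.57 and 0.79).

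The conclusion about overlap rests on the query names. The sizes rest on assumed counts, because the documents give no event rates. The safety tables are descriptive: no hypothesis test, alpha level, sample size or stopping rule uses this row. The change should be made because the category is uninterpretable as labelled and easy to repair, but it does not threaten the trial's main conclusions.

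**What to change.** In SAP 12.6.1:

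1. Delete the venous embolic and thrombotic events query from the bleeding related ischaemic search. Keep the ischaemia queries and preferred terms already listed.
2. Leave the thrombosis or TEE row and tables exactly as they are.
3. Add a rule for remaining events that the TEE query also retrieves. These are arterial events, and infarcts or strokes that the heart and central nervous system searches may find, so deleting queries alone would not separate the categories. Either count such an event as bleeding related ischaemic only if the blinded data review attributes it to bleeding, or present the ischaemic row with and without these events.
4. State that under either option these events always stay in the thrombosis or TEE row, so that reporting of the named thrombosis risk is not weakened.

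The cost is a small programming change and, under the first option, a short review of the overlapping events. The blinded data review meeting already exists (SAP 9.4 and 12.2), though attribution of events would be a new task for it and must be done without knowledge of treatment arm. The second option needs no review. SAP section 3.0 has the plan finalised before database lock, so the change belongs before that point. No new data are collected.

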12.6.2 Deaths and Serious Adverse Events

Listings for SAEs and subjects with AEs with the outcome of death will also be provided for the SAF.

12.6.3 Laboratory Data

The following clinical laboratory variables will be summarized for the overall population, and separately by type of surgery (spinal and abdominal surgery):

Hematology	Red blood cells (RBC), white blood cells (WBC), platelet count, hemoglobin, hematocrit, neutrophils (absolute and %), lymphocytes (absolute and %), eosinophils (absolute and %) and basophils (absolute and %)
Biochemistry	Aspartate aminotransferase, alanine aminotransferase, creatinine, creatinine clearance (Cockcroft and Gault), blood urea nitrogen (BUN), urea, gamma-glutamyltransferase (γ -GT), alkaline phosphatase (AP), total bilirubin, direct bilirubin, indirect bilirubin, potassium, sodium, calcium and chloride
Urinalysis	pH, blood, WBC, protein, glucose, ketone bodies, nitrite, bilirubin and urobilinogen
Markers of Coagulation	PT, INR, aPTT, TAT, F1+2, D-dimer, PS, PC, AT III, TT and ETP(TGT)
Coagulation factors	FII, FV, FVII, FVIII, FIX, FX, FXI, FXIII and vWF

Note: Protein C (PC) is also referred to as Factor XIV. Direct bilirubin and indirect bilirubin are only assessed in case of an elevated bilirubin value and are thus not generally included in statistical summaries.

Quantitative laboratory parameters reported as "< x" or "y" > will be imputed with x/2 and y, respectively, for inclusion in summary statistics. The reported value will be presented in listings.

Descriptive statistics for clinical laboratory values (in SI units) and changes from baseline at each scheduled assessment visit (as stated in Flowchart of study) with the exception of urinalysis parameters and direct/indirect bilirubin will be presented by treatment and treatment arm.

Laboratory results of all hematology, biochemistry, urinalysis parameters and PT/INR, aPTT will be categorized with respect to the laboratory specific reference ranges as normal/abnormal (i.e., high [H], low [L], where applicable). Abnormal values will be further classified with respect to clinical relevance by the investigator. The results and percentages will be summarized by visit and overall for each treatment and treatment arm.

Shifts from baseline to each post-baseline visit for all laboratory variables (except direct and indirect bilirubin) will be summarized by treatment and treatment arm using number and percentage of subjects.

In addition, a shift summary of hematology for number of subjects with change from normal or not clinical significant to clinical significant will be presented.

All the laboratory data will be listed for the SAF.

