#### Special precautions for BT524 administration

All plasma-derived human products may lead to allergic or anaphylactic reactions. Thus, the administration of BT524 will be performed under medical supervision where proper medical care for allergic or anaphylactic reactions can be provided. If allergic or anaphylactic-type reactions occur, the infusion must be stopped immediately. In case of anaphylactic shock, standard medical treatment for shock must be applied.

Prothrombin time PT(INR), activated partial thromboplastin time (aPTT), prothrombin fragments  $F_{1+2}$ , thrombin-antithrombin III complex (TAT), D-dimer, PS, PC, antithrombin III (AT III) activity, thrombin time (TT), thrombin generation test (TGT) and further coagulation parameters are monitored regularly to detect a hypercoagulable state.

Changes in vital signs (including pulse [heart rate], blood pressure, respiratory rate, body temperature) are monitored during the surgery and according to the flow chart (see section III).

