# Surgery Day 1 (end of surgery):

- **Vital signs** (including pulse [heart rate], blood pressure, respiratory rate, body temperature) will be recorded at the end of the surgery.
- Samples for **clinical laboratory parameters** (hematology, clinical chemistry) will be taken at the end of the surgery:
  - **Hematology** (RBC, WBC, platelet count, hemoglobin, hematocrit)
  - Clinical chemistry (ASAT, ALAT, creatinine, creatinine clearance, BUN/Urea, γ-GT, AP, total bilirubin, potassium, sodium, calcium, chloride)
- Sample for **coagulation activation tests** (PT(INR), aPTT, TAT, F1+2, D-dimer, PS, PC, AT III, TT, TGT) will be taken at the end of the surgery.
- Sample for coagulation factors (FII, FV, FVII, FVIII, FIX, FX, FXI, FXIII, and vWF) will be taken at the end of the surgery.
- Sample for plasma **activity of fibrinogen** (Clauss assay) will be taken at the end of the surgery.
- **FIBTEM A10 and MCF** (ROTEM) will be performed at the end of the surgery.
- Start continuous measurement of blood loss until 24 hours post-operative.
- **Amount of blood** from blood suction unit and from swabs, surgical cloths and compresses will be calculated and recorded (blood loss after the decision to treat the subject with IMP until end of surgery).

- **Transfusion products** (allogenic blood products) given intra-operatively will be documented.
- **Concomitant medication or treatment** will be recorded. The type of concomitant medication/treatment, dose/schedule, duration, and the indication the concomitant medication//treatment was given for will be documented.
- **AEs** will be documented.
- Time of end of surgery (time of last suture) will be recorded.
- **Rebleeding episodes** will be recorded.

**Please note:** The following tests have to be doneat the 'end of surgery'. In case the end of surgery is within a short timeframe (< 30 min) after the blood draw '90 minutes after start of first IMP treatment', these tests have only to be repeated based on medical judgment of the investigator.

- Markers of coagulation (Coagulation activation tests)
- Plasma activity of fibrinogen (Clauss assay)
- FIBTEM A10 and MCF (ROTEM)
- Coagulation factors

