## 10.7 Safety Analysis

AEs will be coded using the most current version of Medical Dictionary for Regulatory Activities (MedDRA®). The version used will be defined in the SAP. Incidence rates (i.e., number and percentage of affected subjects) will be calculated for the coding levels *SOC* and *preferred term* and will be presented by treatment arm. Further analyses of AEs will focus on seriousness, intensity, causal relationship to IMP, and outcome. IRAE including SAEs etc. will be displayed in detail.

Safety laboratory assessments (hematology, clinical chemistry, urinalysis and coagulation parameters) will be categorized with respect to the laboratory specific reference ranges as normal/abnormal. Abnormal values will be further classified with respect to clinical relevance. Changes over time will be described by means of "shift-tables" by treatment arm as well as summarized with descriptive statistics by time point and treatment arm.

Vital signs data will be summarized descriptively before and after surgery by treatment arm.

The frequency of thrombosis and of TEEs, virus status, exposure data and concomitant medication will be summarized by treatment arm.

All safety analyses will be based on the SAF.

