Transfusion products				•		•	•	•	•	•	•
Adverse events	•	•		٠		•	•	•	•	•	•

⁶ Test has to be done only 90 minutes after start of 1st IMP administration.
⁷ Total volume and total infusion time (start and end of each infusion) to be recorded.
⁸ Intra-operative blood loss from time-point of decision to treat the patient with IMP until end of surgery.
⁹ Recording of blood loss (drainage volume) until 24 hours after end of surgery.

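### SAP 12.6.3 limits the normal/abnormal and clinical-relevance table to PT/INR and aPTT among coagulation tests, against protocol 10.7 and undeclared, and the SAP flowchart lacks the end-of-surgery coagulation-factor sample

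*SAP*

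**What the plan says.** Protocol 10.7 sets the rule: "Safety laboratory assessments (hematology, clinical chemistry, urinalysis and coagulation parameters) will be categorized with respect to the laboratory specific reference ranges as normal/abnormal". It adds: "Abnormal values will be further classified with respect to clinical relevance". Neither sentence singles out particular coagulation tests. Protocol 9.2.3 lists changes in markers of coagulation and changes in coagulation factors as separate safety endpoints.

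SAP 12.6.3 names the same families of tests for summary, but its classification sentence is narrower: "Laboratory results of all hematology, biochemistry, urinalysis parameters and PT/INR, aPTT will be categorized with respect to the laboratory specific reference ranges". Results classified this way are tabulated by visit and overall, with the investigator's relevance grade for abnormal values.

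SAP 12.6.3 also plans descriptive statistics for laboratory values and "changes from baseline at each scheduled assessment visit (as stated in Flowchart of study"), apart from urinalysis and direct/indirect bilirubin. In the SAP 6.0 flowchart, the coagulation-factor row is marked at baseline, before the first dose and after dosing, with the footnote "Test has to be done only 90 minutes after start of 1st IMP administration". Protocol 7.1, in the end-of-surgery list for PMP subjects, says: "Sample for coagulation factors (FII, FV, FVII, FVIII, FIX, FX, FXI, FXIII, and vWF) will be taken at the end of the surgery".

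**The concern.** The two documents give different rules for analysing a named safety endpoint, and the SAP does not say that it departs from the protocol. The tests affected are the ones that the protocol connects with thrombosis risk. Protocol 6.11 lists PT/INR, aPTT, F1+2, TAT, D-dimer and others, and says that these and "further coagulation parameters are monitored regularly to detect a hypercoagulable state". The same section warns of thrombosis when subjects "are treated with human fibrinogen particularly with high dose or repeated dosing".

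The missing time point bears on repeated dosing. After dosing, the protocol draws coagulation factors only at 90 minutes after the start of the first IMP and at end of surgery, with none on Day 2 or later. Repeated intra-operative administration is allowed. A subject redosed after the 90-minute draw therefore has one factor sample after redosing, the end-of-surgery one, and the SAP schedule does not contain it.

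**Working it through.** No power, alpha or sample-size figure is involved. The check is a count of variables and time points, with the passages set side by side.

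**Step 1. Count the coagulation variables in SAP 12.6.3.**
- Markers: PT, INR, aPTT, TAT, F1+2, D-dimer, PS, PC, AT III, TT, ETP (from the thrombin generation test) = 11.
- Factors: FII, FV, FVII, FVIII, FIX, FX, FXI, FXIII, vWF = 9.
- Total: 11 + 9 = 20, or 10 + 9 = 19 if PT/INR counts as one test.

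**Step 2. See which planned outputs cover them.**

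| SAP 12.6.3 output | Coagulation variables covered |
|---|---|
| Descriptive statistics and change from baseline, at flowchart visits | 20 of 20 |
| Shift tables, baseline to each post-baseline visit | 20 of 20 |
| Listings | 20 of 20 |
| Normal/abnormal and clinical-relevance table | 3 of 20 (PT, INR, aPTT) |

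Left out of the last table: 20 − 3 = 17 variables. With PT/INR as one test: 19 − 2 = 17.

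**Step 3. Look for a declaration.** SAP 4.1 lists changes to the full analysis set, the handling of non-normal data, overall mortality and imputation. It does not mention laboratory classification.

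**Step 4. Compare the coagulation-factor schedules.**

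| Time point | Protocol 4.3 UK | SAP flowchart |
|---|---|---|
| Baseline | yes | yes |
| Before first dose | yes | yes |
| 90 minutes after start of first IMP | yes | yes |
| End of surgery | yes | no |

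The protocol has 4 time points and the SAP 3. After dosing, the protocol has 2 and the SAP 1. The empty SAP cell is unlikely to be an artefact of text extraction. The SAP's end-of-surgery footnote names the coagulation markers and the fibrinogen tests but not the coagulation factors, whereas the corresponding protocol footnote does name them.

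**Step 5. Trace the consequence.** Only the descriptive-statistics sentence in 12.6.3 is bound to the flowchart. Read literally, it plans no end-of-surgery summary for the nine factors. The shift-table sentence has no such tie, and SAP 8.10 defines end of surgery as a study visit, so shift tables may still pick the sample up. However, the SAP defines normal/abnormal categories for only 3 of the 20 coagulation variables, so it does not say which categories the other 17 shift tables would use.

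**Step 6. Check the versions.** SAP 4.0 says the plan was built on protocol versions 4.0 and 4.2 UK. The protocol supplied is 4.3 UK, dated 06-SEP-2021; the SAP is dated 19-JUN-2023, about 21 months later. The protocol's amendment log says version 4.3 added a missing footnote for end-of-surgery coagulation factors. That the flowchart gap comes from a SAP not updated to 4.3 is a reasonable inference, but it is not stated.

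**The case against.** The strongest reply is that very little is lost. All 20 variables keep descriptive statistics, shift tables and listings. The coagulation markers, including TAT, F1+2 and D-dimer, keep their end-of-surgery and follow-up visits in the SAP flowchart. Protocol 9.2.1.4 requires out-of-range values judged clinically relevant to be recorded as adverse events, and SAP 12.6.1 tabulates those, with a dedicated analysis of thrombosis and thromboembolic events. The flowchart gap looks like version lag rather than a decision to drop data. All of this stands, and it limits the point to one table type and one time point. It does not remove the contradiction: the SAP states a narrower rule than the protocol and does not declare it.

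A reader might infer more than the documents support:

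- *That thrombosis-risk laboratory data are left out of the safety tables.* They are not, as the first table above shows.
- *That the FVIII and vWF load of cryoprecipitate would be missed.* Both are summarised at 90 minutes after the start of the first IMP. Protocol 6.2 puts the infusion of two pools at about 30 minutes at a common rate, so that sample falls about 90 − 30 = 60 minutes after a first dose given at that rate.
- *That all factor data after redosing are missing.* The results are listed, and shift tables run to each post-baseline visit.
- *That the absence of Day 5 urinalysis from the SAP flowchart belongs here.* The flowchart-tied sentence excludes urinalysis, and urinalysis is not thrombosis-risk data.
- *That end-of-surgery results must be split by number of IMP administrations.* Neither document requires it, and it would compare groups formed after randomization by how much they bled.

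**Conclusion.** The point holds in a limited form. SAP 12.6.3 contradicts protocol 10.7 for 17 of 20 coagulation variables in one type of table, without declaration in SAP 4.1. The SAP flowchart also omits one of the two post-dose coagulation-factor time points, which removes it from the descriptive statistics if the text is followed literally. Efficacy, alpha and sample size are untouched. It should be corrected before database lock because it concerns the planned analysis of a named safety endpoint.

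The size in practice is uncertain. The number of subjects redosed after the 90-minute draw is not given. The end-of-surgery sample may also be skipped, at the investigator's judgment, when surgery ends less than 30 minutes after that draw. The time-point finding applies to abdominal (UK) subjects only, because the spinal protocol is not among the documents and its schedule cannot be checked.

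**What to change.** 1. Extend the classification sentence in SAP 12.6.3 to all markers of coagulation and all coagulation factors, as protocol 10.7 requires. Alternatively, keep the restriction, and declare and justify it in SAP 4.1.
2. Before extending it, confirm that relevance grades reach the analysis database. Protocol 9.2.1.4 lets investigators grade results in the central laboratory's web tool, and protocol 11.1 says that central laboratory data go to the CRO without saying that the grades go with them.
3. Align the SAP 6.0 flowchart and its footnotes with protocol 4.3 UK for abdominal subjects, so that end-of-surgery coagulation factors enter the descriptive tables. Update the version reference in SAP 4.0.
4. State the shift-table categories for the coagulation variables that currently have none.

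The cost is SAP wording and a few descriptive tables. The samples and the grading are already required by the protocol, so there is no added burden on subjects. The one open item is the transfer of the central-laboratory grades.
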